Plasma storage samples for virology testing			X	X	X	X	X	X	X	X	X	X	X		
Immunogenicity (ADA) serum sample ^k								X		X		X	X	X	X
Serum PK samples (GS-5423 & GS-2872) ^{l, m}								X	X	X		X	X	X	X
Plasma PK sample for LEN ^{l, n}								X	X	X		X	X	X	X
Randomization			X												
HIV Treatment Preference Questionnaire			X		X			X				X			
HIVDQoL			X		X			X				X			
HIVTSQs ^o			X		X			X	X			X			
HIVTSQc ^o												X			
Continue baseline oral ART			X												
LEN oral administration ^p								X							
LEN SC administration								X				X			
GS-5423 IV infusion administration ^q								X				X			
GS-2872 IV infusion administration ^q								X				X			

CCI

ADA = antidrug antibody; AE = adverse event; ART = antiretroviral therapy; ARV = antiretroviral; CD4 = clusters of differentiation 4; CD8 = clusters of differentiation 8; DNA = deoxyribonucleic acid; ECG = electrocardiogram; eGFR = estimated glomerular filtration rate; ESDD = early study drug discontinuation; FSH = follicle-stimulating hormone; HBV = hepatitis B virus; HCV = hepatitis C virus; HIV = human immunodeficiency virus; HIV-1 = human immunodeficiency virus type 1; HIVDQoL = HIV-dependent quality of life; HIVTSQc = HIV Treatment Satisfaction Questionnaire change version; HIVTSQs = HIV Treatment Satisfaction Questionnaire status version; IV = intravenous; LEN = lenacapavir; PBMC = peripheral blood mononuclear cell; PK = pharmacokinetic(s); PSD = post study drug; RNA = ribonucleic acid; SC = subcutaneous; TSH = thyroid-stimulating hormone; Wk = week

- a Screening Visit 2 will be performed once results of GS-5423 and GS-2872 sensitivity testing from Visit 1 are reviewed and participant is deemed eligible to proceed.
- b For participants who discontinue the study prior to Week 52, only a ESDD and 30-day follow-up visit is required. For participants who receive study drug in extension phase, refer to Section 6.3.11 for ESDD and post-ESDD 30-, 90-, 180-, 270-, and 365-day follow-up visits. Counsel participant regarding the importance of continuing a complete ARV therapy in accordance with standard of care, and refer participant to an appropriate HIV treatment facility.
- c Vital signs: blood pressure, pulse, and temperature. On dosing days for LEN + GS-5423 + GS-2872, vital signs should be recorded prior to start of study drug administration and 30 minutes (± 10 minutes) after completion of both GS-5423 and GS-2872 infusion, if coadministered or the GS-2872 infusion, if sequentially administered.

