1.2. Background on Study Interventions

For the purpose of this protocol, study drug will be defined as LEN, GS-5423, GS-2872, and baseline oral ART.

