3.1.1. Randomized Phase

Treatment Group 1

Participants in Treatment Group 1 will receive the long-acting regimen consisting of LEN, GS-5423, and GS-2872.

Participants will discontinue their baseline oral ART following administration of the complete study drugs on Day 1 (SC LEN 927 mg, oral LEN 600 mg, and IV infusions of GS-5423 and GS-2872), and will self-administer oral LEN 600 mg at home on Day 2. Participants will also receive study drug (SC LEN and IV infusion of GS-5423 and GS-2872) at Week 26.

All participants in Treatment Group 1 will return to the study center for visits at Weeks 4, 12, 24, 26, 38, 50, and 52.

Treatment Group 3

Participants in Treatment Group 3 will continue their baseline oral ART through Week 52. After Day 1, participants in Treatment Group 3 will return to the study center for visits at Weeks 12, 26, 38, 50, and 52.

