3.3. Protocol-Specific Discontinuation Criteria

3.3.1. Criteria for Early Discontinuation for the Individual Participants

3.3.1.1. Criteria for Early Discontinuation for the Individual Participant From Study Intervention

Study interventions will be discontinued in the following instances:

- An AE that would, in the judgment of the investigator, affect assessments of clinical status to a significant degree.
 - Following resolution of the AE, the participant may resume study dosing at the discretion of the investigator.
- Unacceptable toxicity, such as a Grade 3 or higher infusion-related reaction to GS-5423 or GS-2872, per Common Terminology Criteria for Adverse Events (CTCAE) grading scale as defined in Section 7.6, or toxicity that, in the judgment of the investigator, compromises the ability to continue study-specific procedures or is considered not to be in the participant's best interest.
- Lack of efficacy: confirmed VF with emergent resistance to study drugs (refer to Section 6.3.9.2).
- Participant request to discontinue for any reason.
- Participant noncompliance.
- Pregnancy during the study; refer to Appendix 11.3.

- Loss to follow-up.
- Discontinuation of the study by sponsor.

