7.7.3.2. Grade 3 Laboratory Abnormality or Clinical Event

- For Grade 3 clinically significant laboratory abnormality or clinical event, study drug may be continued if the event is considered to be unrelated to study drug.
- For a Grade 3 clinical event, or clinically significant laboratory abnormality confirmed by repeat testing, that is considered to be related to study drug, study drug should be withheld until the toxicity returns to Grade 2 or lower.
- If a laboratory abnormality recurs to Grade 3 or 4 following rechallenge with study drug and is considered related to study drug, then study drug should be permanently discontinued, and the participant managed according to local practice including switching to an effective alternative ARV regimen with consideration of the long duration of exposure of study drug and the risk of resistance if viremic. Recurrence of laboratory abnormalities considered unrelated to study drug may not require permanent discontinuation.

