GS-5423 and GS-2872 data on pregnant participants are limited or not available. As per International Council for Harmonisation guidance, monoclonal antibodies directed at viral targets, such as GS-5423 and GS-2872, do not require reproductive toxicity studies. As protein biologics, GS-5423 and GS-2872 are unlikely to have human genotoxicity/teratogenicity/fetotoxicity. A reduction in the clinical efficacy of hormonal contraception is not expected as GS-5423 and GS-2872 are not cytokine modulators and not anticipated to affect the expression of cytochrome P450 enzymes. Please refer to the latest version of the IB for additional information.

2) Contraception Requirements for Participants Assigned Female at Birth and of Childbearing Potential

The inclusion of participants assigned female at birth and of childbearing potential requires using at least an acceptable effective contraceptive measure. They must have a negative serum pregnancy test at screening and a negative pregnancy test on the Day 1 visit prior to the dose of study drugs. In the event of a delayed menstrual period (over 1 month between menstruations), a pregnancy test must be performed to rule out pregnancy. This is applicable also for participants assigned female at birth and of childbearing potential with infrequent or irregular periods. Pregnancy tests will be performed per the study procedures tables ([Table 1](#), [Table 2](#), and [Table 3](#)).

Duration of required contraception for participants assigned female at birth and of childbearing potential enrolled in this clinical study should start from the screening visit until 6 months following last dose of study drug.

Participants assigned female at birth and of childbearing potential must agree to 1 of the following contraceptive methods:

- Complete abstinence from intercourse of reproductive potential. Abstinence is an acceptable method of contraception only when it is in line with the participant's preferred and usual lifestyle.

Or

Consistent and correct use of 1 of the following methods of birth control listed below:

- Hormonal and nonhormonal intrauterine device
- Bilateral tubal occlusion (upon medical assessment of surgical success)
- Vasectomy in the partner assigned male at birth (upon medical assessment of surgical success)

Or

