Participants assigned female at birth and of childbearing potential who initiate use of a hormonal contraceptive greater than 5 days after onset of menses as their method of birth control should use additional backup contraception (eg, condoms) for 7 days or avoid sexual intercourse for 7 days. Hormonally based contraceptives or barrier methods permitted for use in this protocol are as follows:

- Hormonal methods
 - Oral contraceptives (either combined or progesterone only)

- Injectable progesterone
- Subdermal contraceptive implant
- Transdermal contraceptive patch
- Contraceptive vaginal ring
- Barrier methods
 - Male condom (with or without spermicide)
 - Female condom (with or without spermicide)
 - Diaphragm with spermicide
 - Cervical cap with spermicide
 - Sponge with spermicide

Inclusion of methods of contraception in this list of permitted methods does not imply that the method is approved in any country or region. Methods should only be used if locally approved.

Participants assigned female at birth and of childbearing potential must also refrain from egg donation and in vitro fertilization during treatment and until the end of contraception requirement.

3) Contraception Requirements for Participants Assigned Male at Birth

No contraception measures are needed.

4) Unacceptable Birth Control Methods

Birth control methods that are unacceptable include periodic abstinence (eg, calendar, ovulation, symptothermal, postovulation methods), withdrawal (coitus interruptus), spermicides only, and lactational amenorrhea method. A female condom and a male condom should not be used together.

5) Procedures to Be Followed in the Event of Pregnancy

[figure not shown]
Participants assigned female at birth will be instructed to notify the investigator if they become pregnant or suspect they are pregnant at any time from start of the study until at least 700 days following the last dose of study drug. Study drug must be discontinued immediately.

Instructions for reporting pregnancy and pregnancy outcome are outlined in Section [7.4.2.3](#).

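### Because *study drug* is defined to include baseline oral ART, the unqualified order to stop study drug on pregnancy conflicts with the protocol's own instructions to continue or resume ART

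*Protocol*

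**What the plan says.** Protocol Section 1.2 sets the term for the whole document: "study drug will be defined as LEN, GS-5423, GS-2872, and baseline oral ART".

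Section 3.3.1.1 lists, among the reasons to discontinue study interventions, "Pregnancy during the study; refer to Appendix 11.3". Item 5 of that appendix opens with "Participants assigned female at birth will be instructed to notify the investigator if they become pregnant or suspect they are pregnant at any time", a duty that runs from the start of the study to no less than 700 days past the last dose of study drug. It then states: "Study drug must be discontinued immediately". The contraception period in the same appendix "should start from the screening visit until 6 months following last dose of study drug".

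On ART the protocol says several things. Section 3.1.1: "Participants in Treatment Group 3 will continue their baseline oral ART through Week 52". Section 6.2 requires baseline oral ART to be kept up until the Day 1 dosing is complete in Group 1, or the Week 52 dosing in Group 3. Table 2 footnote b, on discontinuation in Group 3, says: "Counsel participant regarding the importance of continuing a complete ARV therapy in accordance with standard of care". Section 6.3.11.1 (Group 1) and Section 6.3.11.2 (both groups, extension phase) send a participant who stops study drug back to baseline oral ART or another regimen the investigator chooses. The Group 3 paragraph of Section 6.3.11.1 gives no ART instruction.

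**The concern.** A stopping rule that says *must* and *immediately* has to be readable without guessing which product it means. Here the defined term covers two things that the protocol elsewhere treats as alternatives: the long-acting drugs, and the oral ART they replace and to which participants return. A site that applied the definition literally would interrupt suppressive therapy in a pregnant control participant. A site that applied the narrower meaning would be departing from the defined term. The same term starts the contraception and notification periods, so their end dates inherit the ambiguity.

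**Working it through.** No figure in the plan is at issue. The check sets the passages side by side and then traces what the SAP would do with the resulting data.

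1. **Is the broad definition in use?** Yes. In Protocol Sections 8.6, 8.6.2 and 8.6.3 the Group 3 safety windows run from the first dose of study drug to 30 days after the last, which in the randomized phase can only mean oral ART. SAP Section 3.1.4 counts continued baseline ART as study drug. SAP Appendix 2 dates Group 3 study drug discontinuation by the permanent stop of baseline oral ART.

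2. **Can the pregnancy rule be triggered in a control participant?** Yes. Table 2 schedules urine pregnancy tests for Group 3 at Day 1, Week 26 and Week 52. The notification duty applies to all participants assigned female at birth, in either group, from the start of the study.

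3. **Group 3, randomized phase.** The only study drug is baseline oral ART. Appendix 11.3 says stop it. Section 6.2 says continue it until Week 52. Table 2 footnote b says counsel on continuing a complete ARV therapy. No visible text says which prevails.

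4. **Group 1, and both groups in the extension.** Stopping study drug is followed by a return to baseline oral ART (Sections 6.3.11.1 and 6.3.11.2). By definition that ART is also study drug, so one instruction stops what the other restarts.

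5. **Follow-on periods.** Six months and 700 days both count from the last dose of study drug. For someone who stays on or returns to baseline oral ART, that last dose has no date, so neither period has a clear end.

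6. **Grade 3 rule (secondary).** Section 7.7.3.2 says that for a related Grade 3 event "study drug should be withheld until the toxicity returns to Grade 2 or lower". The ambiguity is the same, and this bullet names no interim regimen. However, the next bullet mentions switching for recurrent laboratory abnormalities, Section 7.7 requires discussion with the medical monitor, and the content of Appendix 11.5 is not visible in the text available.

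7. **Effect on the analysis.** Inputs: 25 planned in Group 3 (Protocol Section 8.11); Group 3 on-treatment data end 1 day after permanent discontinuation (SAP Section 6); outcome categories from SAP Section 6.1.2.
   - Permanent stop for pregnancy, last on-treatment value < 50 copies/mL, no window data: the outcome is no virologic data. The ≥ 50 count rises by 0. The < 50 proportion falls by 1/25 = 4 percentage points.
   - Temporary Grade 3 withholding: the cut-off is not triggered because the stop is not permanent. A rebound at the last in-window value would count as ≥ 50, again 1/25 = 4 percentage points.
   - Reported results (Protocol Section 1.4.1.2): no participant on a stable baseline regimen had HIV-1 RNA ≥ 50 copies/mL by snapshot at Week 26 or Week 52. Neither route added a control failure at those time points.

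**The case against.** The strongest reply is that the narrower meaning is obvious in context. The part of Appendix 11.3 on drug effects in pregnancy discusses only LEN, GS-5423 and GS-2872. Sections 3.1.1 and 6.2 set study drug against baseline oral ART, and the section on managing virologic rebound (6.3.9.2.1) refers specifically to participants on a long-acting regimen. SAP Section 3.8.1 builds the Group 1 last dose date from the three long-acting agents only and treats a return to ART as a separate restart date. This makes a narrower intent likely. It remains inference against an explicit definition, and the SAP rules are for analysis, not instructions to sites.

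A second reply is that leaving an assigned regimen is compatible with staying on a complete ARV therapy, since a participant could be switched; inclusion criterion 10 requires that a fully active alternative be available. This softens the conflict with footnote b. It does not reconcile the rule with Section 6.2, and the pregnancy instruction itself names no replacement.

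A third reply is timing. Week 52 results are already reported, so the period in which Group 3 takes only oral ART has been analysed, and in the extension Section 6.3.11.2 sends both groups back to ART. That stands. What remains live is the contradiction within the extension and the open-ended follow-on periods.

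A reader might infer that the rule biased the comparison toward the long-acting arm. The documents do not support this: the pregnancy route does not add to the ≥ 50 count, no control failures are reported, and nothing shows that any site stopped ART under this wording. Nor do they support saying that the Grade 3 rule leaves all of the roughly 25 control participants without a regimen: it needs a related Grade 3 event, and the safeguards in step 6 apply.

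**Conclusion.** The contradiction holds on the protocol's own words. Under the Section 1.2 definition, the pregnancy instruction covers baseline oral ART, and no visible text exempts it. The conflict is with Section 6.2 and Table 2 footnote b for Group 3 in the randomized phase, and with Section 6.3.11 for Group 1 and for both groups in the extension. The Grade 3 limb is secondary.

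The reach is every participant of childbearing potential, a number the documents do not give. The possible effect of one control participant on an endpoint is 4 percentage points, taking the planned 25 as denominator; no such effect is shown in the reported results. This is a safety-wording correction, not a design or analysis error.

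The conclusion assumes that no exemption sits in the content missing from Appendix 11.3 (a figure marker stands just before the sentence). The Grade 3 limb also depends on what the missing Appendix 11.5 content says.

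**What to change.** - In Section 1.2, define two terms: the long-acting study drugs (LEN, GS-5423, GS-2872) and baseline oral ART.
- In Sections 3.3.1.1, 6.3.11.1, 6.3.11.2, 7.7.3.2 and 7.7.3.3 and in Appendix 11.3, state which product and which treatment group each stopping, withholding, contraception and notification rule covers, and from which product's last dose each period runs.
- Reconcile these with Section 6.2 and Table 2 footnote b.
- Check the uses of the term in Sections 8.3.1.2, 8.6, 8.6.2 and 8.6.3, so that the Group 3 safety population and windows still refer to baseline oral ART after the split.

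What should happen clinically on pregnancy or after a Grade 3 event is for the sponsor's medical team to decide. The cost is protocol wording and the usual IRB submission under Section 9.2.1. No data collection or analysis changes, because SAP Section 3.1.4 and Appendix 2 already say what counts for Group 3.

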11.4. Toxicity Grading Scale for Severity of Adverse Events and Laboratory Abnormalities

The Division of AIDS (DAIDS) Table for Grading the Severity of Adult and Pediatric Adverse Events, Corrected Version 2.1, July 2017. The DAIDS scale is available at the following location: <https://rsc.niaid.nih.gov/sites/default/files/daidsgradingcorrectedv21.pdf>

11.5. Management of Clinical and Laboratory Adverse Events

AE = adverse event

11.6. Country-Specific Requirements

Not applicable.

11.7. Amendment History

A high-level summary of amendment history is provided in tabular form below. Minor changes such as the correction of typographic errors, grammar, or formatting are not detailed.

A separate tracked change (red-lined) document comparing the previous version of the protocol to this amendment will be made available upon the publication of this protocol.

11.7.1. Amendment 4 (07 Oct 2025)

Rationale for Key Changes Included in Amendment 4	Affected Sections
Added ClinicalTrial.gov Identifier.	Cover page, Synopsis
CCI [REDACTED]	Synopsis; Study Schema, Tables 4 and 5; Sections 1.4.1, and 5.3
Added a study procedure table outlining the extension phase for Treatment Groups 1 and 3 after Week 104 for clarity. Patient-reported outcomes were removed after Week 104 as no further planned use. Electrocardiogram were removed after Week 104. Tables headings were amended to reflect this change. Pharmacokinetic time points and planned interim analysis was updated.	Tables 1, 2, and 3; Sections 6.3.6, 6.3.7, and 8.2.1.1
Weeks 128, and 154 study visits and associated procedures were removed including evaluation of viral load. Viral load will still be assessed at the dosing visits occurring at Weeks 130, 156 and at every 26-week dosing visit during the extension phase. Weeks 130 and 156 visits occur 2 weeks after the removed visits. Viral rebounds from the dosing visits will be managed per protocol.	Tables 1, 2, and 3
Instruction for coadministration infusion was updated for internal consistency with Table 1.	Table 2
For clarity, bNABs/lenacapavir (LEN) was replaced with LEN, GS-5423, and GS-2872.	Section 2
Text updated to clarify that the collection of race and ethnicity data allows for the analysis and reporting of study data by demographic subgroups as required by certain health authorities.	Section 4.1
Confirmation of virologic suppression (human immunodeficiency virus type 1 RNA < 50 copies/mL) from the preceding visit (for example, at Weeks 128 and 154) prior to proceeding with dosing during the extension phase was removed due to the removal of these visits. Participants will still be monitored and managed for viral rebound per protocol at the dosing visit occurring 2 weeks after these removed visits.	Section 5.3

Rationale for Key Changes Included in Amendment 4	Affected Sections
Text aligned with LEN United States Prescribing Information (USPI). Reference to LEN USPI was added.	Section 5.4; Table 6
Added text regarding the responsibilities of the investigator in confirming participant eligibility in response to health authority audit finding.	Section 6.2
Added text regarding appropriate regimen to be followed after early study drug discontinuation (ESDD) and counselling of participants regarding the importance of continuing antiretroviral therapy.	Section 6.3.11
Updated text related to early study drug discontinuation assessments in the extension phase to clarify that participants must be seen 30, 60, 90 and 180 days after ESDD along with a visit every 90 days until 365 days from the last dose of LEN, GS-5423 and GS-2872. Clarified that post study drug visits are the same as post ESDD visits.	Section 6.3.11.2
Added language regarding reporting of any sequelae from a special situation event for clarity.	Section 7.1.3
Clarified text related to death as a serious adverse event for clarity.	Section 7.3.3
Revised serious adverse event (SAE) reporting language to clarify recording and reporting requirements for initial or follow-up SAE data for electronic and paper case report forms.	Section 7.4.1.1
Clarified text that consultation documents and results of investigations obtained by sites will be provided to the sponsor.	Section 7.7.2
“Investigational medicinal product” was replaced with “study drug” for internal consistency.	Section 7.7.3
Pharmacokinetic analysis was updated to include other visits, as applicable.	Section 8.8
Added text to inform that study results will be made publicly available in accordance with local regulatory requirements.	Section 9.2.2
Updated text related to data protection for generalizability to all regions.	Section 9.3.5
Minor editorial and formatting changes.	Throughout, as needed

11.7.2. Amendment 3 (13 May 2024)

Rationale for Key Changes Included in Amendment 3	Affected Sections
Updated the dosage and administration guidance to reflect coadministration option starting at Week 52 (in conjunction with sequential administration).	Study Procedures Table (Tables 1 and 2), Sections 5.3 and 6.3.6
Updated HIV reservoir assay to include peripheral blood mononuclear cells (PBMCs).	Study Procedures Table (Tables 1 and 2)
Sample collection guidance split into 2 footnotes for better clarity (HIV reservoir sample and electrocardiogram data in 1 footnote and biomarker samples [PBMC and plasma] in a separate footnote).	Study Procedures Table (Tables 1 and 2)

Rationale for Key Changes Included in Amendment 3	Affected Sections
CCI	
Updated wording in the risk assessment and risk mitigation plan to align with the current protocol template.	Section 1.5 and Appendix 11.2
Added details regarding management of virologic rebound.	Section 6.3.9.2
Removed details regarding Fisher exact test per decision of Biostatistics group.	Section 8.4
Added section on data protection requirements to align with the standard text in the current Gilead protocol template.	Section 9.3.5
Minor editorial and formatting changes.	Throughout, as needed

